**Table 3: Summary of the study groups and schedule for blood sampling.**

Group	Number to sample	Ages	What and when samples collected				
			BS=blood smear FP=filter paper	BS&FP -when malaria diagnosed	BS&FP -before season	BS&FP -between the second and third MDA each season	BS&FP -dry season/ post intervention (only from select participants)
Child cohort (followed with active case surveillance)	~1800	≤10 yr. olds	BS&FP -when malaria diagnosed	BS&FP -before season	BS&FP -between the second and third MDA each season	BS&FP -post season	BS&FP -dry season/ post intervention (only from select participants)
Households# on village transects (3 villages/arm; ~8 households/village)	~380	all note: ≤10 yr. olds will be sampled in the ACD cohort		BS&FP -before season	BS&FP -between the second and third MDA each season	BS&FP -post season	BS&FP -dry season/ post intervention
PK-PD modeling cohort	180	5-10yo (n=30 per arm) 11-18yo (n=30 per arm) ≥19yo (n=30 per arm)	Each participant sampled for capillary blood up to 5 of the following time points after their last dose of IVM: 0h (pre-last dose), 1h, 4h*, 8h, 12h*, 24h, 48h, 52h, 60h, 72h, 7d*, 14d, 21d and 28d. *venous blood will be collected simultaneously at these time points				
# Hemoglobin analyses will also be performed on the capillary blood from a sub-sample of adults and children over the study using a Hemocue (or other) device.							

Trial monitoring will be according to the Data Safety and Monitoring Plan and an independent Data Safety and Monitoring Board (DSMB) will be established by the DMID to provide safety review and trial guidance, including advice on continuing, modifying or terminating the study. The study monitor will be an in-country contract research organization (CliMAfrica-CRO or other) who will provide external monitoring for the study. During the intervention phase, trained clinical trial monitoring experts from the CRO will conduct at least six monitoring visits (before, during and immediately after the intervention phase of the study, in rainy seasons 1 and 2). These will include assessment of site compliance and standard operating procedures, review of consents, assents, training documents, research/study approvals and data collection forms, review of site facilities, and laboratory sample storage, shipment, and labeling. An interim analysis of the safety data will be conducted after the 2nd MDA occurs in the first rainy season, and also in-between the first and second rainy seasons.

---

## 5. STUDY ENROLLMENT AND WITHDRAWAL

Malaria-endemic villages in southwestern Burkina Faso that will participate in SMC in season 1 of the study will be recruited to participate. The subject population in this region consists of West Africans mainly from the Mossi, Bobo, Dagara, Lobi and Fulani ethnic groups and who are mostly subsistence farmers and traders. All eligible village residents will be asked to enroll, which encompasses people of all ages and genders and reproductive capability, and small to medium size villages ranging between 200-500 people will be recruited; per our power analysis, we require 7 villages per arm and ~100 children who are  $\leq$ 10 years of age per cluster. If possible, we will also attempt to choose villages that have distinct boundaries and non-populated buffer zones of agricultural fields or bush land surrounding them in order to minimize mosquito movement between control and intervention clusters and between study and non-study villages.

### 5.1. Subject Inclusion Criteria

Subjects must meet all the inclusion criteria in order to be eligible to participate in the study. Subject Inclusion and Exclusion Criteria will be confirmed by a study clinician licensed to make medical diagnoses. No exemptions will be granted on Subject Inclusion/Exclusion Criteria in this DMID-sponsored study.

We will attempt to enroll all inhabitants of selected villages who the leaders and majority of village heads-of-household first give their verbal consent to participate in the study.

Inclusion criteria are:

- Residence in selected study village
- Able to understand the information and willing to give consent or assent (age 12-18) and parent/guardian consent if study participant age is  $<$  18 years of age.

We will attempt to enroll all children who live in the selected and verbally-consented villages in our active case surveillance cohort.

Active case surveillance cohort inclusion criteria:

- Residence in selected study village

- ≤10 years of age
- Parent/guardian consent

## 5.2. Subject Exclusion Criteria

Exclusion criteria for participating in the intervention (IVM/placebo MDA):

- Residence outside of the study village
- Height < 90 cm (\*note: if subject becomes ≥90cm over course the trial, this exclusion criteria will no longer be valid in subsequent MDA)
- Current treatment with SP+AQ as part of SMC (restricted to children 3-59 months old) (\*note: if subject discontinuous SP+AQ treatment because they become older than 59 months over course the trial, this exclusion criteria will no longer be valid in subsequent MDA)
- Permanent disability or serious medical illness that prevents or impedes study participation and/or comprehension
- Pregnancy (screened for in women of child-bearing age [ages 12-45] using a pregnancy urine rapid test [e.g. SD Bioline hCG] the week prior to each MDA), as well as older females who have not yet had menopause
- Breast feeding if infant is within 1 week of birth
- Known allergy to ivermectin
- Possibility of *Loa loa* infection as assessed by travel history to Angola, Cameroon, Chad, Central African Republic, Congo, Democratic Republic of Congo, Equatorial Guinea, Ethiopia, Gabon, Nigeria, and Sudan.
- Enrolled in any other active clinical trials

Active case surveillance cohort exclusion criteria:

- Residence outside of the study site
- Permanent disability, serious medical illness that prevents or impedes study participation

---

Additional PK/PD cohort exclusion criteria:

- Concurrent use of drugs known to interfere with CYP3A4 metabolism within the past 14 days. (Section 6.6)
- Hemoglobin < 7g/dL

## 5.3. Treatment Assignment Procedures

### 5.3.1. Randomization Procedures

This will be a cluster (village)-randomized trial. Once the chiefs/leaders and heads-of-households of all fourteen selected villages give their verbal consent to participate following informational and question and answer meetings with the study team, a village representative and the CHWs representing each village will be asked to participate in a public randomization event at the facilities of the district health authority, attended by the district medical director and members of the study team. In front of the attendees, the numbers “1” and “2” will be written on 7 cards each, which will be sealed in identical opaque envelopes, mixed in a container, and then randomly pulled from the container by each village representative. Villages will be assigned to the arm written on the card selected by this representative, and the procedures will be video recorded. These arm designations will be linked to the masked active ingredient tablet or placebo (below).

### 5.3.2. Masking Procedures

The study pharmacist in charge of the drug stock rooms will originate the masking, written on three paper copies and put in identical and sealed opaque envelopes, which will be kept: 1- In the inventory paperwork binder at the drug stock room, and with each PI (2-with [name] in the Investigator’s Brochure, 3- with [name]). The study pharmacist will allocate the IVM and placebo tablets for each IVM MDA round according to the original randomization throughout the trial, and distribute the drug in sealed containers labeled by a code (e.g. “Village X(1-7) – Arm 1” and “Village Y(1-7) – Arm 2”) to the clinical team prior to each round.

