## PROTOCOL SUMMARY

Title:	Repeat Ivermectin Mass Drug Administrations for MALaria Control II (RIMDAMAL II): a double-blind, cluster-randomized control trial for integrated control of malaria.
Phase:	3
Population:	14 villages, 2 arms (7 clusters/arm); all healthy and eligible participants (both genders and all ages), approximately 4,700 people who live in southwestern Burkina Faso
Number of Sites:	1 site in southwestern Burkina Faso
Study Duration:	3 years (between 2018-2021)
Subject Participation Duration:	2.5 years (2019-2021)
Description of Agent or Intervention:	generic ivermectin, 6 mg tablet; dose: 3-day oral regimen of 300 µg/kg/day estimated by height bands, administered monthly for 4 months/rainy season over 2 consecutive rainy seasons.
Objectives:	
Primary:
 

• To assess the impact of a combined approach of repeated IVM MDA and SMC on malaria incidence in children, with the purpose of testing the superiority of IVM compared to placebo for reducing malaria incidence. Our hypothesis that IVM MDAs (the intervention), coinciding with standard of care antimalarial procedures in Burkina Faso (four SMC rounds during the rainy season, maximum LLIN coverage and IPTp for pregnant women), will significantly reduce the incidence of childhood malaria in the intervention arm compared to the control arm. The IVM MDAs will consist of generic IVM or IVM placebo (e.g. Iver P®, Elea Labs; 6 mg tablet) given monthly

from July-October (4X) as a 3-day course to all eligible persons who meet inclusion criteria ( $\geq 90$  cm and not treated with SMC ( $\geq 5$  years), not pregnant or breast feeding an infant less than 1 week old). Dosing of IVM or placebo will be according to height as indicated on the package: 90-119 cm = 1 tablet/day for 3 days; 120-140 cm = 2 tablets/day for 3 days; 141-158 cm = 3 tablets/day for 3 days;  $> 158$  cm = 4 tablet/day for 3 days.

Secondary:

- To measure whether the IVM MDAs will increase harms in the participants
- To measure the entomological indices (mosquito survival rate after blood feeding, mosquito population age structure, sporozoite rate if they are infected with *Plasmodium* parasites, human exposure to *Anopheles* mosquito bites) between the intervention and control arm and over the time of the intervention phase.

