**Table : Treatment Arms**

Arms	Participant population	Intervention
Arm 1	
7 villages; ~2500 participants
 
 
• ~75% will receive the placebo MDA intervention (all eligible persons <math>\geq 90</math> cm not taking SMC (<math>\geq 5</math> years) or pregnant or breast feeding an infant <math>< 1</math> week old).
 
• >700 cohort children <math>\leq 10</math> yrs. of age (~10-children/cluster) followed by active case detection for malaria
 
	standard of care plus placebo MDA
Arm 2	
7 villages; ~2500 participants
 
 
• ~75% will receive the ivermectin MDA intervention (all eligible persons <math>\geq 90</math> cm not taking SMC (<math>\geq 5</math> years) or pregnant or breast feeding an infant <math>< 1</math> week old).
 
• >700 cohort children <math>\leq 10</math> yrs. of age (~100 children/cluster) followed by active case detection for malaria
 
	standard of care plus ivermectin MDA

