**Table 4: Dosing of ivermectin or placebo**

Height (cm)	Estimated weight (kg)	# of Tablets	Total mg per dose	Total mg per 3-day course
90-119	15-25	1 tablet	6mg	18mg
120-140	26-44	2 tablets	12mg	36mg
141-158	45-64	3 tablets	18mg	54mg
>158	65-84	4 tablets	24mg	72mg

The study pharmacist (who will be unblinded) will allocate the IVM and placebo tablets for each IVM MDA round according to the original randomization throughout the trial, and distribute the drug in sealed containers labeled by the codes “Village X(1-7) – Arm 1” and “Village Y(1-7) – Arm 2” to the clinical team no more than 2 days prior to each round.

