### 7.3.1. PK/PD cohort

PK/PD cohort children will be chosen from one control and one intervention village, using the arm code so as not to break the blind. They will be subject to follow-up at an increased frequency. Enrollment criteria are otherwise as for the ACD cohort, with additional exclusion criteria of a 1) hemoglobin <7 g/dL (done by Hemocue or other instrument), and 2) use of concomitant medications (Section 6.6). The total number of participants in the PK/PD cohort is n=180 and participants will be age-stratified. Up to one individual may be enrolled from each age strata within the same household:

- 5-10yo (n=60, 30 from each village-arm)
- 11-18yo (n=60, 30 from each village-arm)
- $\geq 19$ yo (n=60, 30 from each village-arm)

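### All 14 villages share two publicly drawn arm codes, so learning the product in one village unblinds every village, and the Treatment Arms table reuses those labels without saying that it is not the key

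*Protocol*

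**What the plan says.** The Protocol Summary describes "14 villages, 2 arms (7 clusters/arm") and calls the trial double-blind.

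- **The draw (Protocol 5.3.1).** A representative and the community health workers of each village "will be asked to participate in a public randomization event at the facilities of the district health authority", with study team members present and a video recording made. The numbers 1 and 2 "will be written on 7 cards each, which will be sealed in identical opaque envelopes". "Villages will be assigned to the arm written on the card selected by this representative".
- **The key (Protocol 5.3.1 and 5.3.2).** The arm numbers are linked to product in a separate step. The study pharmacist sets the mask and records it in three sealed opaque envelopes, one in the stock room and one with each principal investigator.
- **The labels.** In 5.3.2 the pharmacist will "distribute the drug in sealed containers labeled by a code", with village plus Arm 1 or Arm 2 as an example. In 6.2, under Table 4, the pharmacist will "distribute the drug in sealed containers labeled by the codes", and the same two labels follow with no such qualifier.
- **The table (Protocol Summary, Treatment Arms).** Arm 1 receives "standard of care plus placebo MDA". Arm 2 receives standard of care plus ivermectin MDA.
- **The PK/PD cohort (Protocol 7.3.1).** One control and one intervention village are chosen "using the arm code so as not to break the blind".

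**The concern.** A mask with one code per arm has a single point of failure. Everyone at the draw, and everyone who handles the containers, knows which seven villages belong together. Any reliable sign of the product in one village then carries over to the other 13.

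Two kinds of observation depend on the blind. First, the primary endpoint (Protocol 3.2.1, SAP 2.1.2) counts an episode when a rapid test is positive after either a measured fever or a fever reported over the previous day. The reported route depends on how a nurse asks and how a caregiver answers. Second, adverse-event causality is a clinical judgement (Protocol 8.2.2). Screening, consent and enrolment also follow the draw (Protocol 7.1 and 7.2), and newcomers are approached during the study (5.3.5), so a leak could affect who joins.

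**Working it through.** The plan states no figure for this point, so there is nothing to reproduce. The check is a count of the treatment assignments that an observer must still consider possible.

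**Inputs.** 14 villages, 7 per arm (Protocol Summary); two card values, seven of each, drawn publicly (5.3.1); the same two values on the containers (5.3.2, 6.2).

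**Current scheme**

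1. Before the draw: C(14,7) = 3,432 possible allocations.
2. After the draw: the grouping is known, so 2 mappings remain (1 = placebo and 2 = ivermectin, or the reverse).
3. After the product in any one village is learned: 1 mapping remains, so 14 of 14 villages are unblinded.

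**One neutral code per village, grouping not public**

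1. After the draw: still C(14,7) = 3,432.
2. After one village is learned: C(13,6) = 1,716 allocations of the other 13 remain.
3. If the PK/PD assays identify both of their villages, which are one of each arm: C(12,6) = 924 allocations of the other 12 remain. The current scheme leaves 1.

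**What the table adds.** If the pharmacist's key follows the table's numbering, a reader of the table has the key. If the key was set independently, the table tells the reader nothing. The protocol states neither.

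**Where a sign of the product could arise**

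- Plasma ivermectin is measured in one village per arm, in a single month of either season (7.3.1, 7.4.1). First-season sampling could therefore yield results before the second season.
- Ivermectin is assayed in mosquito blood meals from the houses of PK/PD participants (3.2.2, 7.10.1.2).
- Blood-fed mosquitoes are held for 3 days in the field insectary and scored for survival (SAP 2.2.3).

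**Illustration of the effect on the endpoint.** Assume that nurses who know the arm elicit fever history 10% less often in the ivermectin arm, that the drug has no effect, that test positivity among those tested is equal in both arms, and that the small change in person-time can be ignored. Let f be the share of episodes that qualify on history alone. Measured fever qualifies an episode by itself, so only the share f can be lost:

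rate ratio = (1 − f) + 0.90f = 1 − 0.10f

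| f | Rate ratio |
|---|---|
| 0.2 | 0.98 |
| 0.5 | 0.95 |
| 1 | 0.90 |

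The documents give neither f nor the 10%. For scale, the design assumes a rate ratio of 0.619/1.088 = 0.569 (SAP 1.3), and the preceding trial reported 0.80 (Protocol 2.1).

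**The case against.** The strongest reply is that the plan does have a mask. The pharmacist sets it, the key is sealed, and the arm numbers are tied to product in a separate step. A reader might infer from the Treatment Arms table that opening the protocol is enough to unblind the trial. The documents do not support that: a sealed key would serve no purpose if the table were the key, and the table never claims to be it. What stands is that identical labels are used with no statement that they are independent, so a reader may take the table as the key, rightly or wrongly.

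The assay routes are also less direct than they look. Plasma is frozen and shipped abroad, and blood meals go to a separate US laboratory (Protocol 7.10.1.2), so field nurses do not read those results. Section 14.4 promises care not to break the blind in analyses before the intervention phase ends, and 8.5 confines unblinded review to the closed DSMB session. This shows that no leak has been demonstrated. It does not close the gap, because no section names who receives the assay results or sets a release date.

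A reader might also infer a bias of 10% from the illustration. The value 0.90 is the extreme case, in which no episode has a measured fever. Temperature is recorded at every weekly visit, so the realistic value lies nearer to 1 by an amount the documents do not give.

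Lastly, post-draw enrolment is exposed only if a leak has already happened, and all residents are to be approached (5.1, 7.3). It is a secondary consequence.

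**Conclusion.** The point holds as a fragility in the mask, together with an ambiguity in the labels. With two shared codes and a public grouping, one identified village exposes 14 of 14; with separate village codes it exposes that village and leaves 1,716 allocations of the rest. This rests only on the draw and labelling that 5.3.1 and 6.2 describe.

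It is not established that the Treatment Arms table is the key, that any assay result reaches blinded staff, or that the blind fails as written. The possible effect on the primary rate ratio, between 0.98 and 0.90 for f from 0.2 to 1, is an illustration under an assumed 10% difference in elicitation and not an estimate. Even its extreme is small beside the planned 0.569, but it would be half of the 20% reduction seen in the preceding trial. The change is a cheap improvement that is worth making.

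**What to change.** 1. Keep the public draw, but put 14 unique neutral codes in the envelopes. The pharmacist links seven at random to each product beforehand, on a sealed 14-line list. All 3,432 allocations stay equally likely and the 1:1 ratio is unchanged.
2. Put only the village code on containers, eCRFs, and laboratory and entomology files.
3. Remove the link between arm number and treatment from the Treatment Arms table, or state there that its numbering is unrelated to any code used in the field. Reconcile the table with Protocol 5.3.1, 5.3.2, 6.2 and 7.3.1.
4. Name the already unblinded pharmacist as the person who selects the two PK/PD villages and who supplies arm groupings for closed DSMB reports, including those needed for the arm-level safety thresholds in 8.4.
5. State that plasma and mosquito ivermectin results are withheld from blinded staff until database lock.

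The cost is slightly more work in packing each round and in keeping the list. Sample size, allocation ratio and analysis model do not change. One weakness remains: mosquito survival is seen by village in the field insectary and could still hint at the arm of a sampled village. Separate codes stop that hint from extending to the others but cannot remove it.

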### 5.3.3. Reasons for Withdrawal and Discontinuation of Study Product Administration

Participants (or parent/guardians) may voluntarily withdraw their consent/assent at any stage for study participation without penalty or loss of benefits to which they are otherwise entitled.

An investigator may withdraw a subject from receiving the study product for any reason. Follow-up safety evaluations will be conducted, if the subject agrees. If a subject withdraws or is withdrawn prior to completion of the study, the reason for this decision must be recorded in the case report forms (CRFs).

The reasons, might include, but are not limited to the following:

- Screening error resulting in incorrect enrollment (discovery that the subject did not meet the required inclusion/exclusion criteria)
- Withdrawal of assent/consent at any stage or the subject is not willing to continue in the study (or withdrawal of consent by the parent/guardian to keep his or her child enrolled).
- Suspected or confirmed allergic reaction to the study drugs.
- Safety reasons as judged by the investigators or the DSMB after a meeting to review safety.
- Subject no longer meets eligibility criteria (e.g. becomes pregnant)
- Subject becomes noncompliant
- Medical disease or condition, or new clinical finding(s) for which continued participation, in the opinion of the investigator might compromise the safety of the subject, interfere with the subject's successful completion of this study, or interfere with the evaluation of responses
- Subject lost to follow-up
- Determined by a physician's discretion to require additional therapy not indicated in the protocol to ensure subject's health and well-being (or treatment failure, if applicable)

The investigator should be explicit regarding study follow-up (e.g. safety follow-up) that might be carried out despite the fact the subject will not receive further study product. If the subject consents, every attempt will be made to follow all AEs through resolution. The procedures that collect safety data for the purposes of research must be inclusive in the original informed consent or the investigator may seek subsequent informed consent using an IRB/IEC-approved consent form with the revised procedures.

The investigator will inform the subject that already collected data will be retained and analyzed even if the subject withdraws from this study.

### **5.3.4. Handling of Withdrawals and Discontinuation of Administration**

Participants who discontinue in the study or withdrawal their assent/consent will always be asked about their reason(s) for discontinuing and about any adverse events they may have experienced. If a person discontinues, it should be determined whether:

1. They discontinue treatment, but continue their consent for the data capture and continue follow-up. These subjects will be considered 'off drug study/on study" and follow the same schedule of events except for participation in the interventions.
2. They discontinue all future activities in the study, but continue their consent for the data captured up to that point to be used in the research.
3. They discontinue all future activities in the study and withdrawal their consent for any past data captured to be used in the research.

These scenarios will be recorded in Case Record Forms (CRFs).

